## 1. INTRODUCTION

# 1.1. Background

Melanoma remains the most common cause of skin cancer death in the United States, Europe, and Australia. Despite an evolving understanding of the molecular aberrations and clinical factors that impact outcomes as well as improvements in the therapeutic paradigm, including immunotherapy, metastatic melanoma remains essentially incurable in view of the limited efficacy and the toxicity of the currently available agents. Over the past 10 years, newly approved treatment options with programmed cell death protein 1 (PD-1) blocking antibodies have improved survival outcomes in patients with melanoma, including patients with previously treated unresectable melanoma or treatment-naïve advanced melanoma. Treatment with a single-agent PD-1 blocking antibody resulted in objective response rates (ORR) of 34% to 40%, median progression-free survival (PFS) ranging from 4.1 to 6.9 months, and long-term (5-year) survival rates up to 45% (KEYTRUDA® United States Prescribing Information [USPI]; OPDIVO® USPI; Larkin-2019). When combined with a cytotoxic T-lymphocyte-associated protein 4 (CTLA-4) inhibitor, PD-1 blocking antibody had an ORR of 50%, median PFS of 11.5 months, and long-term survival rate of 52% (OPDIVO® USPI; Larkin-2019). Despite the improved outcomes with PD-1 blocking antibodies, more than 55% of patients do not respond to single-agent nivolumab or pembrolizumab and half do not respond to combination therapy with a CTLA-4 inhibitor. Therefore, there remains a critical need for innovative anticancer therapy in this condition.

There are several preferred Category 1 regimens (based upon high-level evidence and National Comprehensive Cancer Network consensus) available for the first-line treatment of patients with unresectable Stage III/IV melanoma, including PD-1 blockade monotherapy or, if a BRAF V600-activating mutation is present, a combination of agents targeted at BRAF and mitogen-activated protein kinase (MEK) (NCCN-2020). In certain circumstances, nivolumab combined with ipilimumab may be another option.

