## 4.5. Treatment Discontinuation

Treatment discontinuation is defined as any subject who stops receiving study treatment and does not restart within 12 weeks. Subjects who permanently discontinue (for >12 weeks) CMP-001 or nivolumab may not be re-treated with the discontinued study treatment in this study. When nivolumab is permanently discontinued due to an immune related AE, CMP-001 must also be permanently discontinued.

Treatment with study treatment should continue until one of the following occurs:

- Unacceptable AE that precludes further study treatment
- 2 years of study treatment
- PD per RECIST v1.1; continuation of treatment through suspected pseudoprogression is permitted at the Investigator's discretion until confirmed PD per iRECIST
- Upon request of the Sponsor or regulatory agency
- Clinical disease progression in the opinion of the Investigator
- If medically necessary in the opinion of the Investigator
- Subject withdraws consent for study treatment
- Subject has received study treatment for 2 years
- Subject becomes pregnant or begins breastfeeding

- Subject is lost to follow-up
- Death
- End of Clinical Trial

If a subject achieves and maintains a confirmed CR or iCR by Investigator assessment, IT or SC injections of CMP-001 or the combination of CMP-001 and nivolumab may be discontinued at the Investigator's discretion once the subject meets both of the following criteria:

- Subject has been treated for at least 48 weeks (the maximum duration of study treatment is 2 years)
- Subject has received at least 3 doses of assigned treatment beyond the date of the initial CR/iCR

Subjects with PD per RECIST v1.1 as determined by Investigator assessment should remain on treatment and have a follow-up scan performed at least 4 weeks after the initial date of PD to confirm progression per RECIST v1.1 by BICR.

Subjects who discontinue study treatment should complete an EOT visit and 100-day safety follow-up contact, which should occur 100 days (+7) after the EOT or until an alternative cancer treatment is initiated, whichever occurs first (Table 1). Subjects who discontinue study treatment for reasons other than disease progression (either per RECIST v1.1 or iRECIST by Investigator assessment) should remain on study for PTFU (Section 7.6) and receive disease assessments according to the Schedule of Assessments (Table 1).

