# Phase 2/3 Sample Size

If there is a statistically significant treatment difference at a 2-sided alpha level of 0.05 for the ORR at the end of Phase 2, an additional 310 subjects will be randomized in a 1:1 ratio to receive either CMP-001 in combination with nivolumab (Arm A) or nivolumab monotherapy (Arm B). Combined with the 140 subjects enrolled in Phase 2, this will make up the overall Phase 3 study population sample size of 450 subjects.

The Phase 3 sample size of 450 subjects is calculated to compare the PFS by BICR between the 2 treatment arms at an alpha level of 0.05 (2-sided). The final PFS analysis will be performed when at least 331 PFS events have been observed across the 2 treatment arms (PD by BICR review or death from any cause). With 331 PFS events, the study has 90% power to demonstrate a treatment effect in PFS at a 0.05 alpha level (2-sided) when the true HR is 0.70. The smallest treatment effect that can be detected statistically significant in this study is HR 0.805. The sample size calculation is performed in PASS-2020.

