 - Subject Withdrew Consent
 - Lost to Follow-Up
 - o Death
 - Study Terminated by Sponsor
 - End of Clinical Trial
 - Other

Regeneron Pharmaceuticals Inc. / Protocol: CMP-001-011 IQVIA Biotech (Confidential) Project # SZA58924

Subjects will continue study treatment until they reach a reason for treatment or study discontinuation. Percentages of subjects who withdrew for each of these reasons will be calculated using all members of the relevant analysis set as the denominator. Clinically stable subjects may continue study treatment beyond RECIST v1.1 progression based upon Investigator's judgment of potential benefit until PD is confirmed according to iRECIST. The number and percentage of such subjects continuing to receive study drug beyond RECIST v1.1 progression will be presented.

Study treatment may not continue beyond 2 years from initial dose of study treatment. Subjects who permanently discontinue (for >12 weeks) CMP-001 or nivolumab may not be retreated with the discontinued study treatment in this study. When nivolumab is permanently discontinued due to an immune related AE, CMP-001 must also be permanently discontinued.

Time on Study (TOS) will be summarized descriptively. For subjects who are still on study as of the data cutoff date, TOS will be calculated as follows:

TOS (months) = (Data Cutoff Date - First Dose Date + 1) / 30.4375

As for subjects who exited the study on or prior to the data cutoff date, TOS will be calculated as:

TOS (months) = (Study End Date – First Dose Date + 1) / 30.4375

C. Protocol Deviations and Population Inclusions

All protocol deviations will be captured electronically outside of the Electronic Data Capture (EDC) system in the IQVIA Biotech IL-2 system and presented in the tabular manner and as a by-subject data listing. All deviations will be reviewed on an ongoing basis and classified as major or minor following study review process.

D. Eastern Cooperative Oncology Group (ECOG) Performance Status

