Treatment Effect in Non-injected Target Lesions. The treatment effect in non-injected target lesions will be assessed separately from the overall effect. The confirmed ORR in non-injected target lesions based on the RECIST v1.1 Investigator measurements will be summarized for each treatment arm in the ITT Analysis Set using the same approach as that of ORR.

D. Efficacy Analysis on Subgroups of Subjects

The below subgroup analysis (not limited to) for efficacy will be explored using forest plots.

- Age $(< 65, \ge 65)$
- Sex (M, F)
- Baseline ECOG PS $(0, 1, \ge 2)$
- LDH at Enrollment (Elevated, Normal)
- BRAF mutation (Yes, No)
- Number of Lines of Prior Therapies (1, 2, >=3 [categories can be adjusted based on the data])
- Best Response to Prior Anti-PD-L1 (CR, PR, SD, PD, NE, NA, Unknown)

- Clinical Disease Stage at Enrollment (M0/M1a/M1b, M1c/M1d)
- Tumor PD-L1 Expression (TPS: <5%, >=5%)

F. Other Efficacy Related Analysis

Listings of efficacy-related data will include the following:

- All lesion assessments (target lesion, non-target lesion, new lesion)
- Response assessments
- Time to events

IX. Safety Analyses

The assessment of safety will be based on the following assessments, summarized by treatment arm using data from the Safety Analysis Set. Subjects will be analyzed according to the actual study treatment received.

A. Exposure

The number of CMP-001 and nivolumab doses received by each subject will be summarized descriptively by treatment arm for the Safety Analysis Set. The duration of treatment, dose intensities and relative dose intensity will also be summarized separately as follows with descriptive statistics in a tabular manner and a by-subject data listing.

1. Duration of Treatment (DoT)

Duration of treatment (DoT) of CMP-001 and nivolumab will be summarized in a descriptive manner, respectively. DoT will be calculated as follows:

DoT (months) = [min(last dose date + 21, discontinuation/completion date) - first dose date] / 30.4375

Or

DoT (weeks) = [min(last dose date + 21, discontinuation/completion date) - first dose date] / 7

Regeneron Pharmaceuticals Inc. / Protocol: CMP-001-011 IQVIA Biotech (Confidential) Project # SZA58924

2. Dosing Intensities

- (1) Actual dose intensity (mg/week) will be calculated as the total actual cumulative dose received divided by duration of treatment (weeks) for CMP-001 and nivolumab, respectively.

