All other medical occurrences (non-adverse events) that begin before the start of study treatment administration should be recorded on the Medical History/Current Medical Conditions section of the eCRF, not the AE section.

Adverse events starting beyond 100 days after the last dose of the study treatment should not be recorded on the AE eCRF unless they are considered treatment-related SAEs.

Serious adverse events and AEs resulting in discontinuation will be followed until one of the following occurs:

- The event resolves
- The event stabilizes
- The event returns to a baseline value if a baseline value is available
- The event can be attributed to agents other than the study drug or to factors unrelated to study conduct
- The Investigator and Medical Monitor agree that follow-up is no longer necessary

Adverse event (AE) data are available to the Sponsor from two sources, i.e., the eCRFs and the SAE paper forms and corresponding SAE narratives. While reconciliation will be performed to ensure consistency between the two types of data, the production of data summaries and listings will be based on the data collected on the eCRF.

1. Treatment-emergent adverse event (TEAE)

A TEAE is defined as an AE that started or worsened in severity on or after the date and time (if date is the same) when the study treatment was first administered (W1D1) until 100 days after the last dose of the study treatment or until the initiation of an alternative new anti-cancer treatment, whichever occurs first. For cases in which treatment-emergence could not be ascertained, the event will be classified as treatment-emergent. Pre-treatment AEs are AEs that occur from the time of the informed consent prior to the first dose of study treatment (W1D1).

Regeneron Pharmaceuticals Inc. / Protocol: CMP-001-011 IQVIA Biotech (Confidential) Project # SZA58924

TEAEs will be coded using MedDRA (version 23.1 or later) and data will be summarized by treatment arm for the Safety Analysis Set. The number and percentage of subjects reporting any TEAEs will be summarized, as well as the number of TEAEs. A subject with more than one TEAEs within the same level of summarization (i.e., system organ class [SOC] or preferred term [PT]) will be counted only once in that level using the highest severity grade and the strongest causal relationship to study drug for the purposes of the incidence tabulations.

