AEs are graded using Common Terminology Criteria for Adverse Events (CTCAE) version 5.0. AE summaries may include summaries for all AEs and by the maximum CTCAE grade for the item being summarized (i.e., SOC or PT). In these cases, the outputs will include a column for Any Grades as well as columns for the 5 potential CTCAE grades: Grade 1 (Mild), Grade 2 (Moderate), Grade 3 (Severe), Grade 4 (Life threatening or disabling), or Grade 5 (Death).

If a grade is missing for a TEAE, the event will be counted as grade 3 (Severe) in the TEAE summary tables. If a relationship is missing for a TEAE, the event will be counted as related in the TEAE summary tables.

Related AEs include those which are definitely, probably, and possibly related and those with missing relationship.

A TEAE summary table will be generated including the following:

- Subjects with TEAEs
- Subjects with TEAEs of Grade 3 or higher (Grade 3+)
- Subjects with any treatment-related TEAEs
- Subjects with Grade 3+ treatment-related TEAEs
- Subjects with Serious TEAEs
- Subjects with treatment-related Serious TEAEs
- Subjects with TEAEs of Special Interest
 - Immune-mediated adverse event (IMAEs) based on Investigator's assessment
- Subjects with TEAEs leading to Treatment Discontinuation
- Subjects with TEAEs leading to Death

Regeneron Pharmaceuticals Inc. / Protocol: CMP-001-011 IQVIA Biotech (Confidential) Project # SZA58924

In addition, the following TEAE summaries tables will be generated. Percentages will be based upon the number of subjects in each treatment arm of the Safety Analysis Set.

- All TEAEs by MedDRA SOC and preferred term
- Grade 3+ TEAEs by MedDRA SOC and preferred term
- TEAEs by MedDRA SOC, preferred term and maximum severity
- Treatment-related TEAEs by MedDRA SOC, preferred term and maximum severity
- TEAEs leading to Death by MedDRA SOC and preferred term
- Serious TEAEs by MedDRA SOC and preferred term
- Treatment-related Serious TEAEs by MedDRA SOC and preferred term
- TEAEs of Special Interest
- TEAEs leading to treatment discontinuation by SOC, PT and NCI CTCAE grading

A by-subject TEAEs data listing, including SOC, preferred term, verbatim term, severity, outcome, relationship to treatment and action taken will be provided.

2. Adverse Events of Special Interest (AESIs)

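### Adverse events are shown by arm only as crude percentages and raw counts, although each subject's observation window depends on time on treatment

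*SAP*

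**What the plan says.** SAP IX.B.1 opens the treatment-emergent window at first dose and closes it "until 100 days after the last dose of the study treatment or until the initiation of an alternative new anti-cancer treatment, whichever occurs first". Protocol 8.1.3 has the same rule.

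Last dose depends on the course of disease. One reason for stopping in Protocol 4.5 is "PD per RECIST v1.1; continuation of treatment through suspected pseudoprogression is permitted at the Investigator's discretion until confirmed PD per iRECIST". Others include toxicity, withdrawal and clinical progression. SAP VII.B adds a ceiling: "Study treatment may not continue beyond 2 years from initial dose of study treatment".

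The planned displays in SAP IX.B.1 are crude: "The number and percentage of subjects reporting any TEAEs will be summarized, as well as the number of TEAEs". For the tables by organ class and preferred term, "Percentages will be based upon the number of subjects in each treatment arm of the Safety Analysis Set". Immune-mediated events, the only named events of special interest (SAP IX.B.2), are also shown as number and percentage of subjects.

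Exposure is reported separately. SAP IX.A.1 states: "Duration of treatment (DoT) of CMP-001 and nivolumab will be summarized in a descriptive manner, respectively". SAP VII.B summarises time on study, and the death listing in SAP IX.C carries duration of treatment. None of these serves as a denominator for adverse events.

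The SAP governs where it differs from the protocol (SAP I.B). It describes a terminated, exploratory Phase 2 study with 20 subjects randomised and treated, 9 in Arm A and 11 in Arm B (SAP II.C). Safety of the combination relative to nivolumab alone remains a secondary objective (SAP III.B).

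**The concern.** The window rule reads the same for both arms, but its length is decided after randomisation. A subject stopped after one dose is observed for at most 100 days, about 3.3 months. A subject treated for 2 years can be observed for about 27.3 months. With the same monthly risk of an event, the longer-observed group shows a higher percentage with at least one event and more events per subject.

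Raw counts are the most exposed display. Under SAP IX.B each recurrence and each rise in grade is a new event, so counts grow with time observed. They also carry no denominator, and the arms differ in size. Late events, including late immune-mediated ones, depend more on window length than reactions in the first weeks, which fall inside almost any window.

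At stake is how the by-arm safety tables are read. A difference could be toxicity, longer observation, or both, and the planned tables would not separate them.

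**Working it through.** The documents give no figure for this point: no adverse-event hazard and no treatment duration by arm. The calculation below is a sensitivity range, not an estimate for this trial.

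**Inputs**
- Window tail: 100 / 30.4375 = 3.29 months (SAP IX.B.1, with the SAP's own month length). It is shorter if new therapy starts, so tails of 0, 1 and 3.29 months are shown.
- Treatment cap: 24 months (SAP VII.B).
- Arm B time on treatment: the protocol's background section reports "median progression-free survival (PFS) ranging from 4.1 to 6.9 months" for single-agent PD-1 antibodies. This is literature, not a planning value for this trial.
- Arm ratio: the abandoned Phase 3 design was powered "when the true HR is 0.70" (Protocol 9.1). Its event number reproduces: 4 × (1.960 + 1.282)² / (ln 0.70)² = 330.4, so 331.
- Assumptions: treatment ends at progression, exponential times, and the same constant event hazard h in both arms, varied from 0.02 to 0.30 per month.

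**Formulas.** With k = ln 2 / median in Arm B and 0.70k in Arm A:
- mean window = (1 − e^(−24k)) / k + tail
- crude incidence = 1 − e^(−h × tail) × [k / (k + h) × (1 − e^(−24(k + h))) + e^(−24(k + h))]

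**Example** (median 6.9, full tail, h = 0.05): k = 0.1005 in Arm B and 0.0703 in Arm A. Mean windows are 9.06 + 3.29 = 12.35 and 11.59 + 3.29 = 14.88 months, ratio 1.20. Crude incidence is 42.6% in Arm B and 48.4% in Arm A, although the hazard is the same.

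**Full range over h = 0.02, 0.05, 0.10 and 0.30**

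| Arm B median (months) | Tail (months) | Mean window A vs B (months) | Ratio | Excess in A (points) |
|---|---|---|---|---|
| 4.1 | 0 | 8.0 vs 5.8 | 1.37 | 3.5 to 8.4 |
| 4.1 | 1 | 9.0 vs 6.8 | 1.31 | 3.4 to 7.6 |
| 4.1 | 3.29 | 11.2 vs 9.1 | 1.24 | 2.9 to 6.1 |
| 6.9 | 0 | 11.6 vs 9.1 | 1.28 | 3.9 to 8.2 |
| 6.9 | 1 | 12.6 vs 10.1 | 1.25 | 3.8 to 7.5 |
| 6.9 | 3.29 | 14.9 vs 12.3 | 1.20 | 2.3 to 5.9 |

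The excess is about 2 to 8 points. One subject is 1/9 = 11.1 points in Arm A and 1/11 = 9.1 in Arm B, so it is below one subject throughout. The window ratio is also the ratio of expected events per subject. A rate per subject-month has a ratio of 1.00 in every row.

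**Other durations** (fixed, full tail, h = 0.05, equal hazards)
- A 12 and B 6 months: windows 15.3 vs 9.3, event ratio 1.65, crude 53.4% vs 37.1%.
- A 6 and B 9 months: windows 9.3 vs 12.3, event ratio 0.76, crude 37.1% vs 45.9%. The direction reverses.
- Equal durations: no difference.

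**Chance alone.** I drew 9 and 11 subjects from the same distribution (exponential, 24-month cap, full tail) in 200,000 simulated trials. The larger mean window exceeded the smaller by more than 25% in 41% of trials (median 4.1) and 42% (median 6.9).

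**The case against.** The strongest reply is that the effect is small beside the noise. The hazard ratio of 0.70 belongs to a design that was abandoned. At 39% versus 32%, the standard error of the difference with 9 and 11 subjects is √(0.39 × 0.61/9 + 0.32 × 0.68/11) = 0.215, or about 21 points, well above any value in the table. SAP VI calls the analyses mainly descriptive, and no between-arm test of adverse events is specified. Duration per drug, time on study and by-subject listings are all planned, so with 20 subjects a reader can see an imbalance and inspect each case. This stands, and it limits the point to a cheap improvement. It does not remove it: seeing an imbalance is not the same as having a rate that allows for it, and so small a sample makes a chance imbalance in duration likely.

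A reader might go further and infer that the combination arm will look more harmful than it is. The documents do not support that. They give no duration by arm. Treatment may continue past progression, may stop for toxicity, and may stop after a confirmed complete response (Protocol 4.5). If Arm A stops sooner, the distortion favours Arm A. A higher true rate in the shorter-treated arm could also offset it.

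Rates have their own weakness. CMP-001 is given weekly for seven doses and then every 3 weeks, with reactions expected within hours (Protocol 5.1.2 and 5.1.3). In a per-month rate, longer treatment dilutes such front-loaded events. Rates cannot replace the crude tables.

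**Conclusion.** The point holds as a gap in the planned displays. The adverse-event window depends on time on treatment, and no adverse-event table uses time at risk. Where durations differ between arms, crude percentages and counts mix toxicity with observation time.

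The size of 2 to 8 points, less than one subject, rests on a superseded hazard ratio, background medians, exponential times, treatment ending at progression and equal constant hazards. It illustrates the mechanism and does not predict this trial's result. A chance imbalance can exceed it: at 12 versus 6 months the gap is 16 points and 1.65 times the events per subject. Early reactions are little affected. The direction cannot be known from the documents, and nothing here shows that either arm's safety will be misjudged. This is a low-cost improvement, not a flaw that invalidates the safety analysis.

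**What to change.** In SAP IX.B.1, keep all planned percentages and counts. Beside them, for all TEAEs, Grade 3 or higher TEAEs, serious TEAEs and immune-mediated events, add by arm:

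1. Subjects with a first event per 100 subject-months at risk, with an exact Poisson 95% CI. Time runs from first dose to the first event or the end of that subject's TEAE window, or to death, study exit or data cutoff if earlier.
2. Total events per 100 subject-months of TEAE window.
3. Incidence in a common early window of a fixed number of days from first dose, for example Days 1 to 63. It should not end at the W10D1 visit: Protocol 5.1.1 delays dosing visits rather than skipping them, and Protocol 5.1.2 requires all seven weekly CMP-001 doses before the 3-weekly schedule, so dose delays could lengthen a visit-based window in Arm A.

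The cost is a paragraph of SAP text and a few tables from dates already collected. Trial conduct does not change. The intervals will be wide: 3 first events in 70 subject-months give 4.3 per 100, with a 95% CI of about 0.9 to 12.5. The rates assume a roughly constant hazard and dilute early CMP-001 reactions. A footnote should say that they are descriptive and must be read together with the crude and early-window tables.

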Gradable laboratory values will be evaluated and assigned toxicity grades according to the NCI CTCAE v5.0. Clinically significant post-baseline laboratory values will be reported as AEs. When possible, a diagnosis should be recorded as an AE, rather than the symptoms or isolated laboratory abnormalities related to the diagnosis.

Shift tables will be presented to indicate the number and percentage of patients with directional shifts in CTCAE toxicity grades relative to the baseline, when assessing the worst change (i.e., minimum and/or maximum) in the value of each laboratory test during the treatment period. With regard to laboratory parameters without CTCAE toxicity grades (e.g., serum immunoglobulin), similar shift tables will be constructed per normal range to index the shifts above or below the normal range relative to that of the baseline with the categories of < LLN, WNL and > ULN. WNL and normal will be used when appropriate for urinalysis parameters.

Summary statistics will be provided for gradable parameters with either both directions (e.g., hypocalcemia for the low value of calcium and hypercalcemia for the high value of calcium) or only one of the directions as long as the grading criteria are available per the CTCAE. Subjects will be counted only once for each criterion/direction, but the same subject can be counted for both criteria if the subject has laboratory values that meet each criterion. Subjects who meet the criteria of Grade 1 or higher for the high direction will be classified under Grade 0 for the summarization of the low direction if the CTCAE term for low direction

Regeneron Pharmaceuticals Inc. / Protocol: CMP-001-011 IQVIA Biotech (Confidential) Project # SZA58924

exists, and vice versa. Change from baseline will be calculated for each parameter of interest when both the baseline and post-baseline values are non-missing.

Additionally, a summary of Hy's Law criteria will be included to indicate if there is any subject potentially meeting Hy's Law criteria during the study for Liver Function Tests (LFTs). The components of the criteria are as follows:

- ALT or AST >= 3xULN (i.e., upper limit of normal)
- Total Bilirubin >= 2xULN
- ALP < 2xULN

Subjects potentially meeting Hy's Law Criteria is defined as those whose ALT or $AST \ge 3xULN$, Total Bilirubin $\ge 2xULN$ and ALP < 2xULN at the same visit.

2. Changes in Laboratory Values from Baseline

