Hematology and serum chemistry will be summarized in a descriptive manner for the following values that will be derived per unique subject and parameter:

[figure not shown]
- Baseline value
- Minimum post-baseline value and corresponding change from baseline
- Maximum post-baseline value and corresponding change from baseline
- Last post-baseline value and corresponding change from baseline

The baseline value will be determined using the convention described in Section VI.B. In addition, incidence of the most extreme post-baseline laboratory abnormality from the treatment-emergent period will be summarized for the corresponding parameter. A treatment-emergent laboratory abnormality is defined as a laboratory value whose grade is at least one grade higher than the baseline grade.

By-subject data listings of all central laboratory data will be generated, and all values outside the normal range will be flagged as High or Low. Listings of all clinically significant post-baseline laboratory values from local and central laboratory assessments will be presented in the data listings.

Table 3: Clinical Laboratory Assessments

Hematology	Serum Chemistry	Urinalysis	Other Laboratory
			Tests

Regeneron Pharmaceuticals Inc. / Protocol: CMP-001-011 IQVIA Biotech (Confidential) Project # SZA58924

Red blood cells (RBCs)	Alanine	Blood	Coagulation:
White blood cells	aminotransferase	Glucose	Partial thromboplastin
(WBCs)	Albumin	Nitrites	time
Differential WBC count	Alkaline phosphatase	pH	Prothrombin time
Total leukocyte count,	Amylase	Protein	International
including differential	Aspartate		normalized ratio
Hemoglobin	aminotransferase	Specific gravity	
Hematocrit	Bilirubin	WBCs	Thyroid Function
Platelets	Blood urea nitrogen or		Studies:
	serum urea	Microscopic battery:	TSH, T3, free T4 (at
	Calcium	RBCs, WBCs,	Screening)
	Chloride	epithelial cells, casts (only if significant	TSH, with reflexive
	Creatinine	positive findings on	T3 and free T4 if TSH
	Glucose	urinalysis)	is abnormal (on treatment)
	Lactate dehydrogenase		ireatificiti)
	Lipase		Autoimmune
	Phosphorous		laboratory panel:
	Potassium		Anti-doubled stranded
	Sodium		DNA, antinuclear
	Total protein		antibody,
	Total protein		antineutrophil
			cytoplasmic antibody,
			rheumatoid factor, and
			antibodies to ribonucleoprotein
			HIV
			Hepatitis B and C
A11 '	DDC 111 1 11 T	2	nepaulis B and C

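### Two adjacent SAP sentences on two-direction laboratory grading conflict for a subject who is abnormal in both directions of the same analyte

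*SAP*

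**What the plan says.** SAP Section IX.D.1 (Incidence of Laboratory Abnormalities) grades laboratory values by CTCAE v5.0 and summarizes parameters that can be graded in one or both directions. Its own two-direction example is calcium.

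On counting, it says "Subjects will be counted only once for each criterion/direction", and adds that "the same subject can be counted for both criteria if the subject has laboratory values that meet each criterion".

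The next sentence says that anyone reaching Grade 1 or above on the high side "will be classified under Grade 0 for the summarization of the low direction". This is conditional on CTCAE having a low-side term, and the sentence closes with "exists, and vice versa", so the rule also runs from low to high.

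The shift tables in the same section are directional and are built "when assessing the worst change (i.e., minimum and/or maximum) in the value of each laboratory test during the treatment period".

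Section IX.D.2 describes other displays of the same data. For hematology and serum chemistry these include "Minimum post-baseline value and corresponding change from baseline", with a matching line for the maximum. In the by-subject listings of central laboratory data, "all values outside the normal range will be flagged as High or Low".

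**The concern.** The first rule keeps a subject with both kinds of abnormality in both counts. The second is also written about subjects, has no time-point limit and runs both ways. Taken as written, a Grade 1 or higher high value anywhere on treatment removes the subject's low grade, and a Grade 1 or higher low value removes the high grade. The two rules cannot both hold for that subject.

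The graded laboratory incidence and shift tables are at stake. Two programmers working from the same SAP could produce different tables, and the literal version understates toxicity. The second sentence also has no severity threshold: a Grade 3 low value would be shown as Grade 0 if the subject had any Grade 1 high value. The protocol offers no way to settle the matter. Its laboratory section (9.7.2) uses Low, within-normal and High shift categories and has no rule for grades by direction, and SAP Section I.B says that the SAP governs where the two differ.

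**Working it through.** The SAP states no figure here to reproduce. The check applies the Grade 0 sentence to the four possible kinds of subject and compares the results with the sentence before it.

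**Inputs.** For one two-direction analyte, let H be a subject's worst grade among high values and L the worst grade among low values, over all post-baseline visits. The subjects are hypothetical. Arm sizes come from SAP Section II.C: 9 subjects in Arm A and 11 in Arm B, 20 randomized and 20 treated.

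**Three readings of the Grade 0 sentence.**

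- *Literal, subject level, both directions at once:* reported high = 0 if L ≥ 1, otherwise H; reported low = 0 if H ≥ 1, otherwise L.
- *Subject level, high direction applied first:* reported low = 0 if H ≥ 1, otherwise L; then reported high = 0 if the reported low is still ≥ 1, otherwise H.
- *Per value:* each high value is Grade 0 on the low scale and each low value is Grade 0 on the high scale; each direction then keeps its own worst grade, so reported high = H and reported low = L.

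**Results (reported high / reported low).**

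| Subject | H, L | Literal | High first | Per value |
|---|---|---|---|---|
| Normal | 0, 0 | 0 / 0 | 0 / 0 | 0 / 0 |
| High only | 2, 0 | 2 / 0 | 2 / 0 | 2 / 0 |
| Low only | 0, 2 | 0 / 2 | 0 / 2 | 0 / 2 |
| Both | 2, 1 | 0 / 0 | 2 / 0 | 2 / 1 |

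The first three rows are the same under every reading. Only the subject with both abnormalities differs, and the three readings give three different answers. Of these, only the per-value result agrees with the preceding sentence, which counts that subject in both directions. It also fits the use of the minimum and the maximum as separate worst values in the shift tables.

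**Severity example.** With H = 1 and L = 3, the literal reading reports 0 / 0 and the per-value reading reports 1 / 3.

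**Size per affected subject.** Arm A: 1/9 = 11.1%. Arm B: 1/11 = 9.1%. The denominator does not change, because SAP Section VI.L bases percentages on the analysis population and the subject would appear there as Grade 0.

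**The case against.** The strongest reply is that the SAP should be read as a whole. The sentence just before the Grade 0 rule deals with exactly this subject and keeps the subject in both counts. Section IX.D.1 opens by assigning grades to values, its shift tables treat the minimum and the maximum as separate worst values, and Section IX.D.2 defines a treatment-emergent abnormality in terms of a single value. On that view the Grade 0 sentence only explains how someone abnormal in one direction appears in the other direction's table: as Grade 0, not as missing. That is probably its purpose, and it is why the point cannot be put more strongly.

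A reader might infer that the SAP removes such subjects from both tables. The documents do not support that as the plan's outcome. It follows from only one of the three readings, the preceding sentence contradicts it, and even then the subject is shown as Grade 0 and stays in the denominator.

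A reader might also infer that severe toxicity would go unseen. That is not supported either. The minimum and maximum summaries cover hematology and serum chemistry, including calcium; the listings flag all out-of-range central values; and clinically significant post-baseline values are listed and reported as adverse events, which are graded by CTCAE. These displays do not replace a count of subjects by laboratory grade and direction, but they would show the values.

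What does not fall away is the wording. The Grade 0 sentence is about subjects, not values, and does not limit itself to subjects abnormal in one direction only. Where Section IX.D.1 means a single visit it says so, as in the Hy's Law definition. To reach the sensible reading, a programmer must put values in place of subjects.

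**Conclusion.** The two sentences conflict for any subject with graded values in both directions of one analyte. If the second is followed literally, graded incidence is understated in both directions for that subject. This is a stated rule that would give a wrong count, not just a missing detail, so it merits correction.

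Its reach is narrow. Subjects abnormal in one direction or neither are unaffected. The documents give no frequency for subjects abnormal in both directions, so 11.1% (Arm A) and 9.1% (Arm B) are the effect of one hypothetical subject, not an estimate. Those percentages assume that all 20 treated subjects received their randomized treatment, since the Safety Analysis Set is summarized by actual treatment. The analysis is descriptive and exploratory (SAP Section VI), and the SAP attaches no test or decision rule to these tables.

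**What to change.** Reword the Grade 0 sentence in SAP Section IX.D.1 along these lines: *For parameters with CTCAE criteria in both directions, a value graded 1 or higher in one direction is Grade 0 in the opposite direction for that value only. Each subject's worst post-baseline grade is then taken separately in each direction.*

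A subject abnormal in only one direction then appears as Grade 0 in the other table, and a subject abnormal in both is counted in both, as the preceding sentence already says. The same per-value grading should apply to the baseline value used in the shift tables.

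The cost is one sentence in the SAP and a check that the laboratory grading program follows it. No additional data are needed, and results for all other subjects stay the same.
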